4.3.4 Secondary efficacy endpoints analyses

Secondary efficacy endpoints will be tested using a fixed sequence approach to adjust for multiple testing. If the p-value from a test is less than 0.05, the test will be declared as successful and the analysis will continue to the next comparison in the sequence. Formal statistical hypothesis testing will be stopped as soon as a test is accompanied by a p-value ≥ 0.05 . The PPS will be used for the first secondary endpoint for non-inferiority, OT+3 analysis set will be used for the secondary endpoints related to RBC transfusion as rescue therapy, and the ITT analysis data set will be used for all the remaining secondary endpoints.

1. The EU primary endpoint for non-inferiority is the first secondary efficacy endpoint for FDA (see above).

2. Mean change from baseline in LDL cholesterol to week 24 will be analysed using ANCOVA. Baseline Hb and baseline LDL will be used as covariates and treatment groups, CV history, geographic region and dialysis duration as fixed effects. Superiority will be declared if the upper bound of the 2-sided 95% confidence interval of the difference between roxadustat and epoetin alfa falls below 0.
3. Mean change in Hb from baseline to the subjects mean level from week 28 to week 52 in subjects with baseline hsCRP greater than the Upper Limit Normal (ULN) will be analysed analogously as the primary efficacy endpoint. Superiority of roxadustat compared to epoetin alfa will be declared, and this test as successful, if the lower bound of the 2-sided 95% confidence interval of the difference between roxadustat and epoetin alfa exceeds 0 g/dL.
4. Proportion of total time of interpolated Hb values ≥ 10 g/dL from week 28 until week 52 will be estimated for each subject and used as dependent variable. The difference between roxadustat and epoetin alfa will be compared using ANCOVA. Baseline Hb will be used as a covariate and the treatment groups, CV history, geographic region and dialysis duration as fixed effects. Non-inferiority between the groups will be declared, and this test as successful, if the lower bound of the 2-sided 95% confidence interval of the difference between roxadustat and epoetin alfa exceeds -0.15.
5. Proportion of total time of interpolated Hb values within the interval 10-12 g/dL from week 28 until week 52 will be estimated for each subject and used as dependent variable. The difference between roxadustat and epoetin alfa will be compared using ANCOVA. Baseline Hb will be used as a covariate and the treatment groups, CV history, geographic region and dialysis duration as fixed effects. Non-inferiority between the groups will be declared, and this test as successful, if the lower bound of the 2-sided 95% confidence interval of the difference between roxadustat and epoetin alfa exceeds -0.15.
6. The average monthly IV iron use during Week 36 to EOS will be compared between the two treatment groups using a Wilcoxon Rank Sum test. Superiority will be declared if the p-value is less than 0.05.
7. Time-to-first (and proportion of subjects who received) RBC transfusion as rescue therapy, will be analysed using Cox proportional hazard model. The baseline Hb, geographic region, dialysis duration and CV history will be included as covariates. Non-inferiority will be claimed, and this test successful, if the upper bound of the 2-sided 95% CI for the hazard ratio (roxadustat/epoetin alfa) is less than or equal to 1.8.

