7.7.4.2 Erythropoietin analogue administration in patients randomized to roxadustat

For patients randomized to roxadustat, the investigator may initiate use of an approved erythropoietin analogue if all of the following criteria are met:

- A patient's Hb level has not sufficiently responded to two or more dose increases or the maximum dose limit of the study drug has been reached, and
- The patient's Hb is <8.5 g/dL on two consecutive measurements drawn at least five days apart; and
- Clinical judgment does not suggest iron deficiency or bleeding as a cause of lack of response or rapid decline in Hb (see 7.7.4.1 and 7.7.4.2 above for addressing these conditions), and
- Reducing the risk of all immunization in transplant eligible patients and/or reduction of other RBC transfusion-related risks is a goal

The patient is not allowed to be administered both an erythropoietin analogue and study drug at the same time. Treatment with an erythropoietin analogue should be stopped when Hb >9 g/dL or after a 4-week cycle has been completed, whichever comes first. Study treatment should be resumed after the following intervals:

- Two days after stopping epoetin
- One week after stopping darbepoetin alfa
- Two weeks after stopping methoxy polyethylene glycol-epoetin beta (Mircera)

If more than one cycle of erythropoietin analogue rescue is required, the investigator should permanently discontinue study drug. Use of erythropoietin analogues will be recorded in the eCRF.

Note: For patients randomized to epoetin alfa, the investigator may initiate use of a different erythropoietin analogue if clinically indicated. Use of the different erythropoietin analogue will be recorded in the eCRF and will be considered rescue therapy.

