4.1.3 Choice of the non-inferiority margins

Non-inferiority for the Hb efficacy endpoint will be established if the lower limit of the two-sided 95% CI for the difference between the means of the primary endpoint (roxadustat minus control epoetin alfa) is ≥ -0.75 g/dL, see Section 0. In other words, a non-inferiority margin of -0.75 g/dL will be used in the Hb efficacy assessments.

Support for the use of a non-inferiority margin of -1.0 g/dL in the peginesatide submission for the dialysis studies was initially provided by estimating the magnitude of the effect of erythropoietin analogue therapy. This estimate was based on summary information from the darbepoetin alfa development program ([Aranesp 2001](#), [Omontys 2012](#)), with publicly available summary data. Based on these data, the estimated treatment effect of erythropoietin analogue therapy in the dialysis population was approximately 2.0 g/dL. Based on these data, the estimated treatment effect of erythropoietin analogue therapy in the dialysis population with a 10-12 g/dL target range (at least 2.0 g/dL and was considered to be appreciably larger than 1.0 g/dL, thus supporting the choice of a non-inferiority margin of -1.0 g/dL.

Therefore, the choice of -0.75 g/dL as non-inferiority is more conservative than prior programs, and consequently, an appropriate margin to use.

The comparison between the study drugs for the time-to-first instance of receiving RBC transfusion, or erythropoietin analogue (for roxadustat subjects only) as rescue therapy is also based on a NI evaluation. For this purpose, in the lack of support for the choice from the literature, a 1.8 margin has been selected. NI will thus be claimed if the upper bound of the 2-sided 95% CI for the hazard ratio (roxadustat/epoetin alfa) is less than or equal 1.8.

The analysis of the proportion of total time of Hb within the interval of 11 ± 1 g/dL from week 28 until week 52 between the treatment groups also relies on a non-inferiority evaluation. For this purpose a NI margin of -0.15 has been adopted, i.e. the 2-sided 95% CI around the difference between roxadustat and epoetin alfa has to exceed -0.15. No support from the literature has been found for this selection.

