4.3.6 Sensitivity analysis of efficacy endpoints

- The analysis of the primary efficacy endpoint for US will be repeated but will exclude Hb values 6 weeks after the use of rescue therapy. ITT analysis set will be used.
- The analyses of primary efficacy endpoint and the secondary efficacy endpoints will be repeated using the OT+7.
- The analysis of the US primary efficacy endpoint and the Hb related secondary efficacy endpoints will be repeated using the PPS.
- The secondary endpoint of RBC transfusion as rescue therapy will be repeated using the ITT analysis set.
- Change in Hb from baseline using MMRM. Mean change from baseline across all Hb values from week 28 to week 52 will be analysed using baseline Hb as a covariate and treatment group, visit, visit by treatment interaction, CV history, geographic region and dialysis duration as fixed effects. ITT analysis set will be used.

- Proportion of total time of interpolated Hb within the interval of 10-12 g/dL from week 28 to the EOT visit. The difference between roxadustat and epoetin alfa will be compared using an ANCOVA model with baseline Hb as a covariate, and CV history, geographic region and dialysis duration, as fixed effects. ITT analysis set will be used.
- Change in Hb from baseline using PMM – Last Mean Carried Forward, as specified in Section 4.2.8.1. ITT analysis set will be used.
- Change in Hb from baseline using PMM – PMM – Baseline Mean Carried Forward (ANCOVA), as specified in Section 4.2.8.2. ITT analysis set will be used.
- Change in Hb from baseline using PMM – Baseline Mean Carried Forward for roxadustat subjects, MAR assumption for epoetin alfa group (ANCOVA), as specified in Section 4.2.8.2. ITT analysis set will be used.

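### The 1.8 margin and its claim rule are written for transfusion or ESA rescue, but the confirmatory test applies 1.8 to transfusion alone, on treatment, with no rationale for that endpoint

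*SAP*

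**What the plan says.** **Margin.** SAP 4.1.3 says that the comparison of "time-to-first instance of receiving RBC transfusion, or erythropoietin analogue (for roxadustat subjects only) as rescue therapy is also based on a NI evaluation", and that, "in the lack of support for the choice from the literature, a 1.8 margin has been selected". It then gives a claim rule for that composite, based on the upper confidence limit of the hazard ratio.

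**Test.** SAP 4.3.4 item 7, the last step of the fixed sequence, reads: "Time-to-first (and proportion of subjects who received) RBC transfusion as rescue therapy, will be analysed using Cox proportional hazard model". Non-inferiority is claimed "if the upper bound of the 2-sided 95% CI for the hazard ratio (roxadustat/epoetin alfa) is less than or equal to 1.8". The same section states that the "OT+3 analysis set will be used for the secondary endpoints related to RBC transfusion as rescue therapy". Under SAP 4.1.1, OT+3 ends each subject's follow-up three days after the final dose, or at the EOS visit if that is earlier, in both arms. Protocol 8.6.5 item 7 also specifies an on-treatment analysis but gives no margin.

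**ESA rescue.** Protocol 7.7.4.2 allows ESA rescue in roxadustat subjects whose Hb stays low despite dose increases or the maximum dose, where limiting transfusion-related risk is a goal. Study drug resumes after a cycle. However: "If more than one cycle of erythropoietin analogue rescue is required, the investigator should permanently discontinue study drug".

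**Related analyses.** The composite is exploratory, on OT+3 (SAP 4.3.5.2). In SAP 4.3.6, "The secondary endpoint of RBC transfusion as rescue therapy will be repeated using the ITT analysis set", as a sensitivity analysis.

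**The concern.** A non-inferiority margin states how much worse the new treatment may be on a particular endpoint. Here the margin and claim rule belong to one endpoint and the confirmatory test to another, so the SAP contains two claim rules at 1.8 and a rationale for neither.

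The two endpoints can diverge. A roxadustat non-responder given an ESA in place of a transfusion has an event under the composite and none under item 7. If a second ESA cycle is needed, study drug stops for good, and a transfusion more than three days after the last dose is not counted on OT+3 either. At stake is the step 7 claim: it could succeed on treatment while the need for rescue of any kind is greater on roxadustat. Neither the ITT repeat nor the composite can block it.

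**Working it through.** **1. The plan's own figure.** The documents give no power, event rate or event count for the transfusion endpoint. The only stated power is for the Hb primary endpoint (SAP 1.3): at least 99% with 600 subjects, difference −0.30, margin −0.75, SD 1.25 g/dL. It reproduces: SE = 1.25 × √(2/300) = 0.1021; (0.75 − 0.30)/0.1021 − 1.96 = 2.45; power = Φ(2.45) = 99.3%. It has no bearing on item 7.

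For scale, a 1.8 margin with a true hazard ratio (HR) of 1.0 needs 4(1.96 + 0.842)²/(ln 1.8)² = 91 events for 80% power, or 122 for 90% (with 1.282 in place of 0.842). The range of 100–300 events used in step 4 is an assumption.

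**2. Margin and test side by side.**

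| | SAP 4.1.3 | SAP 4.3.4 item 7 |
|---|---|---|
| Event | Transfusion, or ESA (roxadustat only) | Transfusion only |
| Margin | 1.8 | 1.8 |
| Stated basis | None in the literature | None |
| Analysis set | Not stated | OT+3 |

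This mismatch needs no assumption.

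**3. What omitting ESA rescue can hide.** Assume constant hazards and count ESA for roxadustat only, as 4.1.3 does. Let r be the roxadustat ESA-rescue rate divided by the control transfusion rate. Then composite HR = transfusion HR + r. With a transfusion HR of 1.0:

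- r = 0.25 gives a composite HR of 1.25
- r = 0.5 gives 1.5
- r = 0.8 gives 1.8

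At r = 0.8, roxadustat would look equal to control on the tested endpoint and sit exactly at the margin on the endpoint for which 1.8 was chosen. The values of r are assumptions.

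**4. What on-treatment censoring might do.** This is a separate question, about transfusion alone. Suppose the true transfusion HR is 1.8 and a share f of roxadustat transfusions goes uncounted. Let p be the share of roxadustat person-time lost with them; losing a share p of epoetin events instead has the same effect on the ratio.

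- Apparent HR = 1.8 × (1 − f)/(1 − p)
- SE = √(1/d₁ + 1/d₂), with total events D split between arms in the ratio of the apparent HR
- False-claim rate = Φ(ln(1.8/apparent HR)/SE − 1.96)

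Example, f = 0.20, p = 0, D = 100: apparent HR = 1.44; d₁ = 59.0, d₂ = 41.0; SE = 0.203; ln(1.25) = 0.223; Φ(1.097 − 1.96) = 19.4%.

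| f = 20% and | Apparent HR | D = 100 | D = 200 | D = 300 |
|---|---|---|---|---|
| p = 0 (nothing else lost) | 1.44 | 19.4% | 34.2% | 47.6% |
| p = 10% | 1.60 | 8.3% | 12.5% | 16.7% |
| p = 20% | 1.80 | 2.5% | 2.5% | 2.5% |

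The documents fix neither f nor p, so they do not say which row applies.

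**The case against.** The strongest reply is that the test itself is clear. Item 7 states its endpoint, margin and analysis set. Because 1.8 has no literature basis for either endpoint, no composite-specific derivation has been broken. Transfusion is also the more symmetric endpoint, since it is available as rescue in both arms, whereas the composite in 4.1.3 counts ESA for roxadustat only. That stands as a defence of choosing transfusion. It does not supply a reason for 1.8 on transfusion, nor does it remove the second claim rule.

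A reader might go further and infer that OT+3 pulls the hazard ratio down because roxadustat failures leave the risk set. The documents do not support this, for three reasons:

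- OT+3 applies to both arms, and censoring removes person-time as well as events.
- A subject who resumes roxadustat after one ESA cycle stays at risk, and a later transfusion within the OT+3 window counts.
- Epoetin subjects may also move to a different ESA, which the transfusion endpoint likewise ignores.

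It is fair to add that ITT is not a complete remedy. It does not count ESA rescue, and subjects who stop study drug go on to conventional therapy (Protocol 3.9.3), which may draw the hazard ratio towards 1. ITT is therefore useful only as an added condition, with the composite shown as well. Finally, the ITT repeat and the composite are already planned, and item 7 is last in the sequence, so no other claim depends on it.

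**Conclusion.** The point holds as a mismatch between margin and tested endpoint, with a consequence for what step 7 can be said to show. The margin and claim rule in 4.1.3 are for the composite; item 7 tests transfusion alone on treatment; and no basis for 1.8 is given for that endpoint. ESA rescue is not an event and follow-up ends soon after drug is stopped, so on-treatment non-inferiority could be claimed while rescue need is higher.

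The size cannot be fixed from the documents. For f = 20% at a true HR of 1.8, the false-claim rate runs from 2.5% (person-time or epoetin events lost in proportion) to 19–48% (neither lost). These figures rest on assumed event counts and shares and on a normal approximation. The upper end should not be read as an estimate: it deletes roxadustat events while keeping all their person-time and every epoetin event, and nothing in the plan indicates that pattern. Only the step 7 claim is affected.

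**What to change.** 1. In SAP 4.1.3, make the 1.8 margin and claim rule name the endpoint tested in item 7, state the basis for 1.8 on that endpoint, and delete the composite claim rule.
2. In SAP 4.3.4 item 7, claim non-inferiority only if the OT+3 analysis and the ITT analysis already planned in 4.3.6 both have an upper 95% limit at or below 1.8. Requiring both can only make the claim harder to win.
3. Present the composite result from 4.3.5.2 beside the claim, because transfusion on ITT still does not count ESA rescue.
4. Reconcile the definition of rescue. Protocol 7.7.4.2 treats a different ESA in the epoetin arm as rescue, whereas Protocol 5.1.1.2 and SAP 4.1.3 confine ESA rescue to roxadustat, and SAP 4.3.5.2 does not say which applies. The composite depends on the answer.

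The cost is SAP wording and reconciliation of the rescue definition across the two documents; no new analysis is needed. The downside is that the step 7 claim becomes slightly harder to win.

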3.5 Methods for assigning treatment groups

Randomization schedules will be prospectively prepared. Automated randomization and treatment assignments will be provided by an IWRS /IVRS. The randomization codes will be computer generated by AstraZeneca R&D using GRand (AZ Global Randomization system) and loaded into the IVRS/IWRS database. A blocked randomization schedule by country will be produced.

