7.7.3 Supplemental iron use

Oral iron supplementation is allowed for both treatment arms without restriction. Oral iron is recommended for dietary supplementation to support erythropoiesis and as the first line for prevention and treatment of iron deficiency, unless the patient is intolerant to this route of treatment.

In subjects receiving roxadustat, the investigator may initiate the use of an approved IV iron supplement if:

- A patient's Hb level has not sufficiently responded to two or more dose increases of study drug, and
- Ferritin <100 ng/ml or transferrin saturation (TSAT) <20%

Study treatment may continue during IV iron administration. Discontinuation of IV iron supplementation is recommended once the patient is no longer considered to be iron deficient (ferritin >100 ng/mL and TSAT >20%). Use of IV iron will be recorded in the eCRF. In subjects receiving epoetin alfa, IV iron supplementation will be given according to standard of care.

In addition to scheduled assessments (Table 1) iron indices may be assessed anytime (via central lab) to evaluate iron storage status of the patients, if considered necessary by the investigator.

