1.2.3 Stratification variables

The randomization in this study will be stratified by country. The stratification variables for the other studies in the program will be used in the analyses for this study as covariates, with addition of incident vs stable dialysis. The stratification variables are:

1. Baseline Hb (≤ 10.5 g/dL vs > 10.5 g/dL)
2. cardiovascular/cerebrovascular/thromboembolic medical history (Yes vs. No)
3. geographical region (US vs. Ex-US)
4. incident vs. stable dialysis (dialysis duration ≤ 4 months vs > 4 months from the randomization date)

Baseline Hb will be included in the analyses as a continuous covariate, hence, not as a dichotomous factor, unless specified otherwise. Throughout this document, the variable cardiovascular/cerebrovascular/thromboembolic medical history will be shortened as CV history, and the variable incident vs stable dialysis will be shortened as dialysis duration

CV history at baseline will be defined for subjects with history of any of the following diseases:

- Myocardial infarction
- Percutaneous coronary intervention
- Coronary artery bypass
- Cardiac failure congestive
- Ischaemic stroke
- Haemorrhagic stroke
- Cerebrovascular accident

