3.1.5 IV iron related secondary efficacy variables

The use of IV iron will be investigated with the variable:

- Average monthly IV iron use per subject during, week 36 to EOS (monthly defined as a period of 4 weeks).

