4.1.1	
The criteria to censor at PACD has been removed.
 
Subjects will be censored at the EOS instead of EOT for FAS.
	To harmonize with the censoring rules of the PSAP.
4.1.4	Deleted Section “Investigation of informative censoring”.	Not applicable since the CV analyses will not be performed for the individual CSR.

4.2.6	Decreased the number of multiple imputations to 200 from 1000.	To reduce the computational runtime.
Subsections of Section 4 related to statistical analyses on CV Safety	
Removed the statistical analyses of the adjudicated CV events from this SAP.
 
Deleted section “Model checking”.
	
All analyses of CV safety will be conducted in accordance with the PSAP, and will not be done for the individual CSR.
 
Not applicable since the CV analyses will not be performed for the individual CSR.

Subsections of Section 4 related to statistical analysis on efficacy	
The section on primary efficacy endpoint analysis is split into two sections, one for US FDA and the other for EU health authority.
 
The primary efficacy endpoint designated for EU health authority is added as the first secondary efficacy endpoint designated for US FDA
 
Changed the ordering of the secondary efficacy endpoints.
 
The PPS will be used for the first secondary endpoint, OT+3 analysis set will be used for the secondary endpoints related to RBC transfusion as rescue therapy, and the ITT analysis data set will be used for all the remaining secondary endpoints.
 
Changed the analysis model of IV iron to Wilcoxon Rank Sum test.
 
Analyses of the exploratory efficacy endpoints newly added in Section 3 are specified accordingly.
	
To harmonize with the primary variables of the other phase III studies in the program
 
To harmonize with the secondary endpoints of the other phase III studies in the program. A decision based on balancing clinical importance of different endpoints together with the likelihood for success.
 
To better the fit the distribution of the IV iron data.
 
Analyses of interest

	The analysis data sets of individual sensitivity analyses are updated, and new sensitivity analyses are added.	To harmonize with the sensitivity analyses of the other phase III studies in the program

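### Randomisation is blocked by country, but the confirmatory IV-iron test is an unstratified Wilcoxon: valid, but mildly conservative if country drives IV-iron use in both arms

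*SAP*

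**What the plan says.** - **Randomisation.** Protocol 3.5: "A blocked randomization schedule by country will be produced". SAP 1.2.3: "The randomization in this study will be stratified by country". No other randomisation factor is named.
- **Covariates.** SAP 1.2.3 continues: "The stratification variables for the other studies in the program will be used in the analyses for this study as covariates", with incident versus stable dialysis added. The resulting list is baseline Hb, CV history, region (US vs Ex-US) and dialysis duration. Country is not on it.
- **Endpoint.** SAP 3.1.5: "Average monthly IV iron use per subject during, week 36 to EOS (monthly defined as a period of 4 weeks").
- **Test.** SAP 4.3.4 item 6: the endpoint "during Week 36 to EOS will be compared between the two treatment groups using a Wilcoxon Rank Sum test", with superiority declared at p below 0.05, in the ITT set. It is sixth of seven secondary tests in a fixed sequence at two-sided 5% (SAP 4.2.2), so a miss ends formal testing before RBC transfusion (item 7).
- **Reason for the Wilcoxon.** SAP 6.1, Table 4: "To better the fit the distribution of the IV iron data". Stratification is not discussed.
- **IV-iron rules.** Protocol 7.7.3: "In subjects receiving epoetin alfa, IV iron supplementation will be given according to standard of care". For the other arm: "In subjects receiving roxadustat, the investigator may initiate the use of an approved IV iron supplement if" two stated conditions are met.

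**The concern.** The primary analysis and secondary items 1 to 5 and 7 are all model-based and carry the four listed covariates. Item 6 alone carries nothing.

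Blocking by country keeps the arms balanced within each country, so between-country differences in IV-iron practice largely cancel out of the treatment contrast. The unstratified Wilcoxon still counts those differences in its null variance. If country affects use in both arms, the variance is too large for the design: the test rejects less often than 5% under the null and loses power under the alternative.

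A country effect is plausible because the outcome is itself a treatment practice, in about 250 centres worldwide. Nothing elsewhere in the SAP covers the gap. The OT+7 repeat in SAP 4.3.6 changes only the analysis set, and the exploratory IV-iron comparisons in SAP 4.3.5.5 copy item 6. At stake is some power for the IV-iron claim and, through the sequence, the chance to test transfusion formally.

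**Working it through.** **1. The plan's own figure.** The documents state no power or effect size for IV iron. The only stated figure is for the primary endpoint (SAP 1.3): at least 99% power with 600 subjects, difference -0.30, margin -0.75, SD 1.25. Check: Φ(0.45 / (1.25·√(2/300)) - 1.96) = Φ(4.41 - 1.96) = 99.3%. It reproduces, but says nothing about item 6.

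**2. Direction, analytically.** Let R be the share of rank variance lying between countries, equal in both arms. With exact balance within country, the true null variance of the rank sum is about (1 - R) times the nominal one, so

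- size = 2·[1 - Φ(1.96/√(1-R))]
- power = Φ(θ - 1.96/√(1-R)), where θ is the noncentrality of the country-stratified test.

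With θ = 2.80 (80% for the stratified test):

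| R | 1.96/√(1-R) | Size | Wilcoxon power |
|---|---|---|---|
| 0.05 | 2.011 | 4.4% | 78.5% |
| 0.10 | 2.066 | 3.9% | 76.9% |
| 0.20 | 2.191 | 2.8% | 72.9% |

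Exact balance overstates the effect, because the endpoint starts at week 36 and some subjects will have no data by then. If 80% remain at random, the within-country arm imbalance has variance n·0.8·0.2, against n·0.8 under simple randomisation. One fifth of the between-country variance therefore returns, and (1 - R) becomes (1 - 0.8R). Size is then 4.1% at R = 0.10 and 3.2% at R = 0.20.

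**3. Size of the loss, by simulation.** From the documents: about 2000 subjects, 1:1, blocked by country. Assumed: 18 countries, 30% of subjects in the US, blocks of 4, 80% evaluable after week 36, 40 to 46% with zero use, countries with fewer than 20 evaluable subjects pooled within four regions. The outcome is a country effect plus N(0,1) noise minus a shift for roxadustat, left-censored. Country share is measured before censoring. There were 4000 replicates per cell. Country effect equal in both arms, power at a 0.15 SD shift:

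| Country share | Wilcoxon size | van Elteren size | Wilcoxon power | van Elteren power | Gain (points) |
|---|---|---|---|---|---|
| 5% | 4.3% | 4.7% | 75.9% | 77.1% | 1.2 |
| 10% | 4.1% | 5.0% | 73.7% | 76.6% | 2.9 |
| 20% | 3.8% | 5.0% | 70.0% | 76.5% | 6.5 |

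A second run at 0.15 SD gave Wilcoxon size 4.6% and 3.5% at shares of 10% and 20%, and power of 75.4 versus 78.1% (2.7 points) and 70.8 versus 76.8% (6.0 points).

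**4. Dependence on the treatment effect (equal country effect).** The gain at shares of 10% and 20% is 3.8 and 7.3 points at 0.10 SD, 1.3 and 2.7 at 0.20 SD, and 0.4 and 0.7 at 0.25 SD, where both tests exceed 98% power.

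**5. Other assumptions, equal effect, shares of 10% and 20%.** With 10 countries at 0.15 SD: 2.7 and 5.8 points. With 30 countries: 2.3 and 7.4. With about 65% zeros and a 0.175 SD shift: 2.5 and 5.3.

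**6. Is blocking the cause?** In a separate simulation with R about 0.22, Wilcoxon size was 3.6% under country blocking and 4.8% under simple randomisation. The conservatism therefore comes from leaving the blocking out of the analysis.

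**7. Where stratifying does not help (0.15 SD, 10,000 replicates).** Country explains nothing: 78.5% Wilcoxon, 78.1% van Elteren (-0.45 points, SE 0.15). Country acts only under epoetin alfa, 10% share: 83.1% versus 82.4% (-0.66, SE 0.18). Across all epoetin-only cells the difference was -0.7 to +0.3 points.

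**8. Intermediate case.** No figure is given for a country effect that is weaker, but present, under roxadustat. In this censored model, unequal country variance also moves the arm means: at a nominal 0.10 SD shift, the mean difference rises from 0.057 to 0.091. The treatment effect is then not held fixed and the cells are not comparable across shares. The same applies to absolute power in the epoetin-only cells, which are used only to compare two tests on the same data.

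**The case against.** The strongest counter-argument is that the equal-effect condition is not the likeliest one. Protocol 7.7.3 leaves IV iron to standard of care only under epoetin alfa; under roxadustat, one protocol rule governs its start in every country. A country effect that is weaker or absent in that arm is plausible, and the gain is then small or nil. This stands and limits the point.

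Second, the IV-iron effect may be large. Protocol 1.1 lists reduced IV-iron need as a potential advantage, and the arms follow different rules. At 0.25 SD or more the choice of test hardly matters. This also stands.

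Third, no confirmatory analysis uses country, so changing only item 6 could look selective. A reader might infer from SAP 1.2.3 that omitting country breaks the SAP's own rule. It does not: that section promises the sister studies' factors plus dialysis duration, not country. The case for item 6 is narrower. It has no adjustment at all, and the stated reason for the Wilcoxon, the data's distribution, is met equally well by a stratified rank test.

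Fourth, replacing a confirmatory test late in an open-label trial invites questions: the SAP amendment is dated 28 September 2018 and completion was estimated for Q3 2018. That is a reason to fix the change before lock without sight of IV-iron data by arm.

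Finally, the choice matters only if the primary test and items 1 to 5 all succeed and the two tests fall on opposite sides of 0.05. That bears on importance, not correctness.

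**Conclusion.** The point holds as an optional improvement in efficiency. Item 6 is valid as written. A reader might infer that ignoring the randomisation factor biases the comparison or inflates type I error; neither follows, since the error is towards conservatism.

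If country affects IV-iron use similarly in both arms, size is about 4.1 to 4.6% at a 10% country share and 3.5 to 3.8% at 20%. The power loss is about 3 and 6 points at an effect giving the stratified test about 77 to 78% power. The loss is negligible at 0.25 SD or more, small if the country effect is weaker under roxadustat, and about nil if it is confined to epoetin alfa.

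A large loss might also be inferred, but it would need both a high country share and equal effects in the two arms, and the documents support neither. Country share, IV-iron effect, number of countries, block size, share of zeros and attrition are all assumptions. The primary endpoint, the EU endpoint and items 2 to 5 are unaffected; item 7 is touched only through its place after item 6.

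**What to change.** Before database lock, and without looking at IV-iron data by arm, replace the test in SAP 4.3.4 item 6 with a van Elteren test stratified by country.

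- Pool countries below a pre-set size within the four regions of SAP 4.3.7. Set the threshold on counts blind to treatment arm, preferably randomised subjects, so that it does not depend on post-randomisation data.
- Keep the unstratified Wilcoxon as a sensitivity analysis.
- Use the same test for the exploratory IV-iron comparisons in SAP 4.3.5.5 that refer to item 6.
- Carry the change into Protocol 8.6.5 item 6 or record it in SAP section 6, which currently declares no changes from the protocol.
- Leave the MI-ANCOVA, MMRM, other ANCOVA and Cox analyses as planned; their covariates were chosen for harmonisation with the other studies.

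The cost is a sentence of SAP wording, a pooling rule and a note that the decision was made blind to arm; no new data are needed. The power cost is about 0.5 points if country explains nothing and about 0.7 if it acts only under epoetin alfa.
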